1.3 Justification for Pilot Study

Cameroon's national policy recommends that OPV0 and BCG be administered as soon as possible after birth. While coverage rates for BCG (84%) and OPV0 (79%)¹⁰ are relatively high in Cameroon, it is estimated that these vaccines are often administered weeks or months after birth,¹¹ not within the timeframe recommended for their administration or that which will be needed for a successful HepB-BD program (<24 hours after birth).¹² Currently, most health facilities do not administer vaccines every day, but rather only on designated immunization days. With babies being born every day, this poses a challenge to reach newborns via the current immunization service delivery system. Based on the study conducted in 2019 that highlighted the barriers and facilitators of timely birth dose administration, the Ministry of Public Health with support of CHAI decided to pilot facility specific HepB BD integration programs. A component that arose from the 2019 study that was of key concern was the lack of communication and integration between the immunization and maternity wards. Thus, this pilot work proposes a facility-based approach to better integrate birth dose vaccination into the broader facility-based maternity and newborn care processes to ensure newborns born within facilities are vaccinated within the recommended timeframe. While the previous assessment and studies have identified many common barriers to timely birth dose administration, the purpose of this work is to focus on the feasibility of integrating the birth dose vaccine process into maternity practices.

¹⁰ EPI administrative data 2018

¹¹ Chiabi A., Nguefack F., Njapndounke F., Kobela M, Kenfack K, Nguifack S., Mah E, Nguefac-Tsague G., Angwafo F., (2017). Vaccination of infants aged 0 to 11 months at the Yaounde Gynaeco-obstetric and pediatric hospital in Cameroon: how complete and how timely?. *BMC Pediatrics*. 2017. 17:206. DOI 10.1186/s12887-017-0954-1

¹² WHO (2015). A Guide for Introducing and Strengthening HepB-BD Vaccination. www.who.int/immunization/documents

2 Methodology

[figure not shown]
2.1 Study Design

This is a three-part intervention study; baseline, implementation and final assessment. The purpose of this feasibility assessment is to report on the quantitative findings of an intervention integrating immunizations into maternity and newborn care across 15 health facilities in Cameroon. The overall aim is to assess the feasibility of administering OPV0 and BCG birth doses within 24 hours of birth in Cameroon:

- 1) Baseline data collection (4 weeks to complete)
- 2) *Intervention implementation* including health care worker training, and ongoing monitoring of the project (*12 weeks to complete*)
- 3) Final assessment to gather an end line estimate of the outcomes (4 weeks to complete)

The figure below is a graphic representation of the study outline.

Figure 1: Outline of pilot study

This pilot study is expected to take 20 weeks (see appendix 5.1 for a detailed project timeline) not including initial preparations such as obtaining ethics approval and training of data collectors. There is a possibility for delays due to an increase in COVID-19 pandemic. The study team will ensure the proper conduct of the study while respecting strict barrier measures.

2.2 Study sites

Health facilities across Cameroon are classified under six categories namely: category one: General hospitals, category two: Central hospitals, category three: Regional hospitals, category four: district Hospital, category five: Medicalized Health centers and category six: Integrated Health centers. We purposefully selected 15 health facilities from these categories. These health facilities were also selected from three regions based on their dissimilar characteristics in geography, culture and immunization coverage. We also selected a mix of public and privately owned as well as semi-rural and urban health facilities. For the purpose of this study, we define semi-rural health facility as one serving a community that depends predominantly on agricultural activities for subsistence. For logistic reasons, more facilities were selected in the center region. Study sites selected are as follows:

Adamawa	Center		West	West	
1.	Hospital Protestant de	4.	Hôpital Nicolas Barre	13.	HD Mifi
	Ngaoundéré	5.	HD Biyem Assi	14.	HD Foumbot
2.	CMA de Mbe	6.	HD Obala	15.	CSI Catholique
3.	CMA Dibi	7.	Centre Medical Marie Reine Etoudi		Baham
		8.	HD Cite Verte		
		9.	CS Catholique Nkoabang		
		10.	CMA Ahala		
		11.	CS Deo Gracia, Nkolbisson		
		12.	CSI Urbain Mbalmayo 2		

Table 1	1: List	of	study	sites	by	region
---------	---------	----	-------	-------	----	--------

2.3 Study Period

The study is scheduled to take place for 20 weeks between January and April 2021.

2.4 Study Population

The study population will include:

- All babies received in the maternity unit, or EPI unit for OPV0 and/or BCG vaccines in the 15 study facilities, during the 1-year baseline period and the intervention period;
- HCW from the 15 facilities involved in either EPI or maternity and newborn care

2.5 Site selection criteria

The 15 health facilities will be selected based on the following inclusion and exclusion criteria while ensuring a mixture of semi-rural and urban, and large and small facilities, private and public facilities to observe feasibility and challenges across different levels of health care. Below are the proposed facilities purposefully selected through an iterative process with key stakeholders and EPI regional managers.

Table 2: Site selection criteria

Characteristics of health facilities selected	Urban setting	Semi-rural district
High volume (Above 100 average monthly deliveries)	Hôpital Nicolas Barre	HD Obala
(Above too average monthly deriveries)	HD Biyem Assi	
	HD Mifi	
	Hospital Protestant de Ngaoundéré	
Medium volume	Centre Medical Marie Reine Etoudi	CS Catholique Nkoabang
(50 – 100 average monthly deliveries)	HD Cite Verte	CMA de Mbe
		HD Foumbot
Low volume	CMA Ahala	CMA Dibi
(Below 50 average monthly deliveries)	CSI Catholique Baham	CS Deo Gracia, Nkolbisson
		CSI Urbain Mbalmayo 2

Inclusion criteria:

- Facilities providing maternity and newborn services including immunization services
- Facilities with either functional cold chain equipment with reliable power sources on site OR those located within one km of the district or another facility with cold chain equipment on site for easy access

Exclusion criteria:

- Facilities participating in research or interventions that will impact the outcomes measured
- Facilities experiencing higher than normal demand of COVID-19 patients will be excluded to not overburden HCWs further and potentially impact ongoing services
- Health facilities that participated in the 2019 birth platform assessment

2.6 Facility sensitization and workflow creation and vaccine availability

Study staff will introduce the purpose of the study to the selected study sites and gain permission to conduct the study overall. Study staff will set up a time to meet with the facility to discuss the process of integration and discuss facility-specific situations. A workflow of facility-specific integration will be proposed and further refined during the intervention training.

Further, vaccines available to the EPI units will be used for this study. No vaccines or consumables will be procured separate from the usual channels. Currently, EPI has the following vaccines in stock at the central, regional, district and health facility stores.

Vaccine	Manufacturer	Country
BCG	GreenSignal Biofarma Pvt Ltd	India
BCG	BB-NCIPD Ltd	Bulgaria
bVPO	Bharat Biotech	India
bVPO	GlaxoSmithKline	Belgium

Table 3: Details of vaccines (BCG and OPV) currently available at EPI

2.7 Training Sessions

2.7.1 Intervention training

Training sessions will be held at each of the 15 facilities separately, with the same study members leading the sessions. Rather than a central training, we will conduct training at each facility, thus reducing mass gatherings during the COVID-19 pandemic. Please see the infection control section (Section 3.2) for COVID-19 related processes during training. At each individual training, all relevant and available health staff, including EPI focal points and maternity and newborn staff, will be asked to participate. In facilities where not all staff are able to attend training, we will ensure at least 1 staff member per shift is able to attend, to enable the information to be passed down to all staff members. During the touch points with the facility, staff will assess if the information was indeed passed down. The sessions will be split into two half day to prevent the facility from closing for a day and to allow for staff to be properly distanced. Moreover, training sessions will be held outside where possible. Ahead of training, a member of the study team will discuss potential training dates with the facility in-charge, ensuring dates occur when most convenient for the staff. The principal investigator will ensure that participants are comfortable throughout training and data collection. The training session will incorporate the below components.

Table 4: Summary of components included in training session

Training Component	Details
Maternity and newborn clinical protocols	 Knowledge reinforcement for topics relating to birth dose immunizations including: Immunization basics (Note: the HCW participating in the study are anticipated to be well-versed in this already, however we can leverage modules from Vaccination in Practice training to provide targeted refreshers based on the audience) Birth dose vaccine information for OPV0 and BCG including safety information and contraindications

	 Immunization technique including vaccine handling and site of administration Directly address hesitancy surrounding opening a multi-dose vaccine vial for only 1 baby by sharing PEV policy on opening vials for one child as well as training on practices to carry this out effectively (e.g. updating wastage rates in forecasts for ordering, calculating shelf life once opened, etc.) Reinforce incorporating birth dose conversations into routine antenatal care visits and adding messaging into ANC talking points 		
Roles and responsibilities of different providers	Outline detailed roles and responsibility for each HCW involved in birth dose vaccinations. Develop and train on facility-specific work flows (see section 2.5 above) which will orient HCW to how the birth dose administration fits into maternal and newborn care in terms of sequencing of services, process for recording and reporting and collecting the vaccines (see below), and mitigation plans and reminders (e.g. to follow safe newborn checklist and best practices in terms of handling emergencies first, etc.)		
Policy for birth dose administration	Provide information on updated policy for the birth dose vaccines to be administered in the maternity unit.		
Cold chain storage planning	During the baseline assessment, study members will assess each maternity unit's 24/7 access to a working refrigerator for vaccine storage. Each facility will have a plan (as part of the integrated workflow) on how to access the vaccines immediately after a birth takes place and will be outlined. For facilities without cold chain equipment, a daily schedule (including weekends and holidays) will be implemented where a morning trip is		
	made to the closest health facility or district health service with CCE to pick up vaccines and an evening trip is done to return unused vaccines to the same health facility.		
Recording and reporting harmonization	To ensure birth doses vaccines are properly recorded in both facility records and for the purposes of this pilot study, two record changes will take place and will be described in detail.		
	Birth dose maternity reporting form For the duration of the pilot study maternity units will be provided with a simple recording form with space to document each birth and information on birth doses given. Scenarios for accurately filling out the form will be discussed.		
	Updated birth registry		

	The birth registry will also be updated to include a column to check if the baby received the birth doses of BCG and OPV0 within 24 hours. At the end of each day, this paper will be brought to the EPI unit to incorporate into their record books. In addition, child health cards will need to be stored in maternity units so caregivers can acquire the book at the time of the birth dose administration, and the updated birth dose information is recorded on the health card.
Out of facility births	We will use this opportunity to brainstorm strategies to address birth dose timeliness among out of facility births for future studies.

Contingency plan:

In the event of worsening COVID-19 pandemic, the pilot study will be restricted to facilities that have already completed training sessions and the intervention for the remaining facilities will be on hold until it is safe to continue with the intended pilot study.

2.7.2 Data collectors training

Training for baseline will occur for this group approximately 1 week before data collection begins and will last for 3 days. The data collection training will cover the purpose of the study, methods in quantitative data collection, electronic data collection methods, ethics, and a thorough review of the data collection tools. The training will be didactic with role-playing scenarios and data collectors practicing the data collection tools on example registers. A refresher for end line data collection and any changes in language will be emphasized in a morning review before data collection. In addition to training required for this pilot study, training will also cover COVID-19 transmission information and the importance of avoiding touching one's face, shaking hands, and safe coughing and sneezing etiquette. For additional information on infection control, please see section 3.2. Guidelines for reporting all illnesses to study staff and refraining from working when sick will be outlined. The infection control plan for each data collection activity outlined in this protocol will also be discussed and hard copies shared with data collectors to ensure they are aware of expectations.

In the final day of training, the data collectors will pilot the data collection tools in 2 health facilities. Through the pilot, any changes or edits in data collection tools will be incorporated.

Contingency plan:

In the event of worsening COVID-19 pandemic that occurs before data collection training, the pilot study will be on hold until it is safe to continue.

2.8 Ongoing trouble-shooting touch points

To enable touch points to discuss problems during the 12-week intervention and foster a relationship between the study team and maternity staff, ongoing monitoring of the intervention will occur. Due to

COVID-19, this will be occurring remotely. Every two weeks the head of the delivery unit will take a photo of the birth dose maternity reporting forms and send it to the study team for review of progress. Once the photo is obtained a brief telephone conversation will occur to troubleshoot immediate challenges, check on the pilot study progress, and to further strengthen the relationship.

Contingency plan:

In the event of worsening COVID-19 pandemic and facilities see a large increase in case load, scheduling the phone meetings will be delayed until it is reasonable to continue.

2.9 Data Sources and Collection

2.9.1 Birth registry and immunization registry

To obtain accurate data on birth dose timeliness, the birth registry and immunization registry will be utilized (Section 5.4). At each birth maternity staff record birth details into a birth register which includes the newborn's first and last name, date of delivery, type of delivery, complications, sex, and date of discharge (however, it is common for not all sections to be fully completed). Each health facility also maintains an immunization registry containing information on each child and all vaccinations given at the facility with the corresponding date. The baseline and end line assessment of timeliness are each expected to last two weeks and will consist of data collectors visiting each facility and collecting information using electronic data collection and tablets. Two methods will be employed to capture different indicators around timing of administration for birth dose vaccines. Both will utilize registry extraction of the immunization register and birth register. Data collectors will ask permission before utilizing the registers and assure that the data collection will not disrupt ongoing facility activities.

Age of babies at time of receiving birth vaccines (BCG and OPV0) – Immunization registry extraction

At baseline:

Data extraction for children in the immunization register will occur by using a sampling interval to ensure children are sampled throughout the entire year. The sampling interval will be created by taking the total number of children entered into the immunization register for the previous 12 months and dividing by our required sample size (N = 30). For instance, if 90 children were entered into the register in the past 12 months, the sampling interval will be 3; if only 30 children were entered into the register in the past 12 months, the sampling interval will be 1. With the sampling interval, the data collector will count backwards from the most recent entry in the immunization register and begin gathering data. The data collector will record the name, date of birth, and record the date(s) of immunization for each of the birth vaccines in the immunization register. Using the name and date of birth, the data collector will then cross-check with the maternity registers to confirm that same child's date of birth. Records that are missing either a date of immunization or date of birth will be recorded to help determine how many children were potentially born out of the facility, or have incomplete records, but will not count towards the total desired sample size for timeliness coverage. Data collectors will continue working backwards through the registers entering data for every Xth child (according to the sampling interval) until they have successfully recorded the

date of immunization and date of birth for 30 children. If they reach the end of the year without entering complete data on 30 children, the data collector will be instructed to loop back through the year but start now on the second child registered when counting.

At end line:

The end line registry extraction will utilize the same sampling technique as baseline. The same sample size (N = 30) will be used with the sampling period being the duration of the study period.

Proportion of babies born in facilities receiving birth dose vaccines within 24 hours – Maternity registry extraction

At baseline:

The same sampling interval/methodology described above will be utilized again, only this time the data collectors will begin with the birth registers to determine their sampling interval. Then this interval will be used to pull names first from the birth register to select a sampling of babies that were born in that specific facility and then cross-checked with immunization dates for birth vaccines in the immunization registers. Records that are missing either a date of immunization or date of birth will be recorded to help determine how many children were not vaccinated at that facility or lack complete records. Data collectors will continue working backwards through the registers entering data for every Xth child (according to the sampling interval) until they have successfully recorded the date of birth and date(s) of immunization for 30 children.

At end line:

The end line registry extraction will utilize the same sampling technique as baseline. The same sample size (N = 30) will be used with the sampling period being the duration of the study period. As there will be children who may not receive their birth dose vaccines before the end line data collection, this indicator will focus on those children who did/did not receive the vaccine within 24 hours.

Contingency plan:

In the event of worsening COVID-19 transmission, facility staff will locate the relevant registry pages and will send photo records of the pages to study staff. Study staff will then continue with data extraction as outlined.

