2.11 Data Analysis

All outcomes will be descriptive in nature with the intent to assess preliminary impact and not statistically significant findings. For both measures of timing of birth dose vaccines, we will compare the facility-level value at baseline to end line of the intervention. Basic statistics (means and proportions) will be performed on the HCW surveys and the new birth dose reporting forms. Information and recommendations reported in open-ended questions from HCW surveys may inform final recommendations of the project but only at an aggregated level and would not be published, shared, or reported at the individual level.

To identify indications of COVID-19 impacting in-facility births, we will use the information contained in the DHIS2 over the last 2 years to compare historical yearly birth trends for the 15 included facilities, with the trends we observed during this pilot study. Due to the small sample size of health facilities and short nature of this study any potential findings of changes in time trends will be descriptive in nature. During check-ins with the facilities the team will also document other factors due to the pandemic that may impact the study such as stock outs or changes on guidance. As this data is not formally gathered, this will be documented and descriptive in nature. Please refer to study tool "Notes for touch point calls" in Section 5.4 that will gather informal information about the health facility-specific processes.

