For sampling interval, count how many children are entered within a year of today's date. Divide this total number by 30 to get your sampling interval. For instance, if there are 300 children within the year, your sampling interval is 300/30 or 10. Therefore, you will enter every 10th child until you reach 30 children in total. For this work you will also be looking the child up in the immunization register. Please ask the in-charge and the EPI nurse to gather this information when it is not in use.

	Delivery register			Immunization register									
Child Name	Q1. Date of Birth	Q2. Date of OPV0 administered	Q3. Date BCG administered	Q4. Were you able to find this child based on name	Q5. Date of OPV0 administered	Q6. Date BCG administered							
	A - Date of birth listed? 1 = Yes, 2 = No (If no, skip Q1.B)	A – Was vaccine administered? 1 = Yes, 2 = No (If no, skip Q2.B)	A – Was vaccine administered? 1 = Yes, 2 = No (If no, skip Q3.B)	and birth date in the register? 1 = Yes, 2 – No (if no, skip Q5 and Q6)	A – Was vaccine administered? 1 = Yes, 2 = No (If no, skip Q5.B)	A – Was vaccine administered? 1 = Yes, 2 = No (If no, skip Q6.B)							
	B - Date listed C – Time of Birth	B - Date listed C – Time of vaccine administration	B - Date listed C – Time of vaccine administration		B - Date listed C – Time of vaccine administration	B - Date listed C – Time of vaccine administration							

Newborn data tool

This form should be used to record data about each delivery during the study period. Data should be completed by a delivery nurse and shortly after the baby is discharged.

Child #:	Facility		Date:	//
	Code:			

Delivery Inform	nation	OPV0→	
Gender	Male1 Female2	OPV0	Yes1 No2
Date of birth, Time of birth, and birth weight	/ : : (DD/MM HH:mm) Grams	DATE AND TIME THE BABY RECEIVED OPVO	/ : : (DD/MM hh:mm)
CIRCLE ALL SERVICES PROVIDED	EPI visitA Dr visitB PNCC OtherX If other, specify:	IF NO, PLEASE CIRCLE THE PRIMARY REASON	Caregiver refused1Stock out2Scheduled for later3EPI was not open4Left before receiving the vaccine6Too few children to open a vial7Not eligible for clinical reasons8Not enough time for vaccination9Other10If other, specify:
OXYTOCIN GIVEN?	Yes1 No2	BCG→	
DISCHARGE DATE AND TIME	/ :	BCG	Yes1 No2
PLEASE LIST ANY CC	MPLICATIONS OR COMMENTS ON THE BIRTH:	DATE AND TIME THE BABY RECEIVED BCG	/ ::
		IF NO, PLEASE CIRCLE THE PRIMARY REASON	Caregiver refused

Notes for touchpoint calls

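### Both end line register samples may reach back before training, and the mean-age sample includes late doses to babies born before it on any reading, so the change in mean age is not a clean measure of impact

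*Combined protocol and SAP*

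**What the plan says.** Section 2.9.1 describes two register extractions per facility. The age indicator samples entries in the immunization register, counting back from the latest. The 24-hour proportion samples births in the maternity register. At end line each repeats the baseline technique, "with the sampling period being the duration of the study period". For the age sample, no rule refers to the training date or the date of birth.

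On what that period is, the sections differ:

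- Section 2.1 makes the first phase "Baseline data collection (4 weeks to complete", followed by 12 weeks of intervention and 4 of final assessment.
- Section 2.3: "The study is scheduled to take place for 20 weeks between January and April 2021".
- Section 5.4 puts training in week 5 and end line extraction in week 17.
- Section 2.4 defines the babies studied as those seen "during the 1-year baseline period and the intervention period".

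Section 2.11 compares each facility's baseline and end line values on both timing measures and calls the outcomes "descriptive in nature with the intent to assess preliminary impact and not statistically significant findings". Section 2.9.1 recognises limited follow-up only for the 24-hour indicator. Sections 2.11 and 2.14 do not raise it for age.

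**The concern.** A before-after comparison reads as an effect of the intervention only if the after sample consists of babies the intervention could have reached. Two groups here do not qualify.

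The first is doses given, and births occurring, before the facility was trained. They enter only if the study period means all 20 weeks, but then they affect the primary proportion as well as the mean age.

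The second is babies born before training who come late for vaccination after it. Section 1.3 says these doses are often given weeks or months after birth, so this group need not be small. It enters the age sample whichever way the period is read, because sampling is by register entry.

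At stake are Objective 3, a key indicator in Table 5 and, on the longer reading, the primary outcome. A real shift to early vaccination could look much smaller than it was.

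**Working it through.** **The plan's own figure.** 4 + 12 + 4 = 20 weeks, as stated.

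**Weeks before training.** Extraction at the start of week 17 leaves 16 weeks. Counting from the start of training week 5, 4 of 16 (25%) come before; counting from its end, 5 of 16 (31%).

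**Primary proportion, 20-week reading.** Assume even births, the full window sampled, 5% within 24 hours before training (section 1.1 reports 4% for BCG and 7% for OPV0 in 2019) and a true 50% after:

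- 5 and 11 weeks: (5 × 5% + 11 × 50%) / 16 = 35.9%
- 4 and 12 weeks: (4 × 5% + 12 × 50%) / 16 = 38.8%

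**Mean age.** The documents give no delay distribution, so this part is assumed. Births are one per day. A share of 0.05 is vaccinated at age 0 before training and p after. All others have exponential delays with mean m0 (born before training) or m1 (born after). The window runs from A days before to T days after training. Write E0 = exp(−T/m0) and E1 = exp(−T/m1).

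| Entries | Number | Summed age |
|---|---|---|
| Dated before training | A | 0.95·m0·A |
| After, at age 0 | p·T | 0 |
| After, late, born before | 0.95·m0·(1−E0) | 0.95·[2m0²(1−E0) − m0·T·E0] |
| After, late, born after | (1−p)·[T − m1(1−E1)] | (1−p)·[m1·T − 2m1²(1−E1) + m1·T·E1] |

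Central case: m0 = m1 = 30 and p = 0.5. The true mean falls from 0.95 × 30 = 28.5 to 0.5 × 30 = 15.0 days, a fall of 13.5. For A = 35 and T = 77, E0 = E1 = 0.0768:

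- Numbers: 35 + 38.5 + 26.3 + 24.7 = 124.5
- Summed ages: 997.5 + 0 + 1410.2 + 412.8 = 2820.5
- Mean: 2820.5 / 124.5 = 22.7 days; fall seen 5.8 of 13.5, or 43%

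Dropping the first row: 1823.0 / 89.5 = 20.4 days, a fall of 8.1, or 60%.

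| Window, days before / after training | End line mean | Share of fall seen | Range of share | Entries from babies born before training |
|---|---|---|---|---|
| 35 / 77 | 22.7 | 43% | 38-54% | 49% |
| 28 / 84 | 22.1 | 48% | 40-60% | 44% |
| 0 / 77 | 20.4 | 60% | 50-78% | 29% |
| 0 / 84 | 20.2 | 62% | 50-79% | 28% |

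The range covers m0 = m1 of 14, 30, 45 or 60 days and p of 0.3, 0.5 or 0.7.

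**If late delays change** (m0 = 30, p = 0.5):

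- Lengthening to 45 days: the true fall is 6.0 days; 5.2-5.7 is seen with the full window (87-95%) and 7.3-7.5 with entries after training only (122-124%).
- Shortening to 20 days: the true fall is 18.5 days; 6.7-7.4 or 9.2-9.5 is seen.

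**No effect** (p = 0.05, m0 = m1 = 30): the mean is 28.5 in both periods, so there is no false signal.

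**Splitting entries by birth before or after training.** With no effect and the 0 / 77 window, the two groups average 53.6 and 15.5 days. The born-after group looks young only because its late doses have not yet happened.

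**The case against.** The best case for the plan has four parts.

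*The window is already limited.* Section 2.4 names the intervention period. The newborn form in section 5.3 says "This form should be used to record data about each delivery during the study period", although section 2.7.1 introduces that form at training, so study period may loosely mean the weeks after training. This stands as far as it goes: inclusion of doses and births before training is conditional on the 20-week reading. It does not remove late doses to babies born earlier.

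*The draw may not reach back that far.* Collectors count backwards and stop at 30 complete records, and rounding of the interval is not specified. Rounded down with all records complete, 59 entries give an interval of 1 and reach the latest 30/59 = 51%; 89 give 2 and reach 60/89 = 67%. Both stop short of training, since the weeks after it are 69-75% of the window. The full-window figures therefore assume a full pass.

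*The outcomes are descriptive.* True, and section 2.14 disclaims precision. But section 2.11 still uses the comparison to assess preliminary impact, and that use is what the mixture affects.

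*The size is assumed.* Correct. The documents fix neither the delays nor the uptake after training.

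Three stronger readings are tempting and unsupported. A reader might infer that the fall in age must be understated; the 45-day case shows that it can be overstated. A reader might infer that the primary proportion is certainly diluted; that holds only on the 20-week reading. A reader might infer from the one-year instruction on the printed tools that end line looks back a year; section 2.9.1 gives end line its own period, and the tools carry the baseline instruction.

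**Conclusion.** The concern holds in limited form and is worth correcting. The sections conflict on the end line window, and the conflict covers both register samples. If the 20-week reading is followed and fully sampled, the primary proportion is diluted (50% reads as about 36-39% under the stated assumptions).

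Whichever reading applies, the change in mean age mixes babies the workflow could reach at birth with babies it could not. With late delays unchanged, about 38-60% of the true fall is seen with the full window and 50-79% with entries after training only. Direction and size depend on delays that the documents do not give. The register mean remains a legitimate description of ages at vaccination in calendar time; it does not isolate the effect of the intervention.

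**What to change.** 1. **One window (section 2.9.1).** For both samples, run it from that facility's own training to extraction: register entries for the age sample, births for the 24-hour sample. Align section 2.4 and the end line tools. Settle the extraction dates too: section 2.9.1 says "The baseline and end line assessment of timeliness are each expected to last two weeks", whereas section 5.4 marks only week 17 at end line.
2. **Interpretation (sections 2.11 and 2.14).** Keep mean age as a calendar-time description. State that it still contains late doses to babies born before training and is not a clean measure of effect. Reconcile Objective 3, which covers every baby vaccinated at the facility, with section 2.14, under which babies born elsewhere do not contribute. Do not split entries by birth before or after training.
3. **Optional addition, not a replacement for average age.** From the birth-register sample, report the proportions with BCG, and with OPV0, recorded at the facility by days 7 and 28, among births with at least 28 days of follow-up in both periods and whether or not a dose is found. In the central case these go from 25% and 63% to 60% and 80%. With no effect and equal recording they stay at 25% and 63%.

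Items 1 and 2 cost only wording. Item 3 uses date fields already on the tools but has three downsides:

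- **Fewer births qualify.** Only 77 − 28 = 49 to 84 − 28 = 56 days of births are eligible, so about 19-20 of 30 spread over all births after training. At 30.4 days a month, 30 eligible births need about 19 deliveries monthly (16 with 56 days). Table 2 lists five facilities as "Below 50 average monthly deliveries"; any below those figures would use all eligible births.
- **Vaccination elsewhere.** Those babies count as not vaccinated at the facility.
- **Recording.** Training also changes the birth register and the daily transfer to EPI records (section 2.7.1, Table 4), so better recording alone could raise these proportions.
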